8.2 Selection of Study Population

Patients who complete Protocol MSK-002 or who have demonstrated benefit after completing the dose titration period but failed to meet randomization criteria for MSK-002, and who meet the inclusion and exclusion criteria for participation in the current study will be eligible.

8.2.1 Inclusion Criteria

Individuals eligible to participate in this study must meet all the following inclusion criteria:

1. Participated in the MSK-002 study
2. Willing and able to provide written informed consent after the nature of the study has been explained and before the start of any research-related procedures.
3. Female patients of childbearing potential must have a negative pregnancy test (urine human chorionic gonadotropin [HCG] at the end of MSK-002 study); and must practice an effective, reliable contraceptive regimen during the study and for up to 30 days following discontinuation of treatment.
4. Ability to participate in the study based on overall health of the patient and disease prognosis, as applicable, in the opinion of the Investigator; and able to comply with all requirements of the protocol, including completion of study questionnaires.

8.2.2 Exclusion Criteria

Individuals who met any of the exclusion criteria in the original protocol or those listed below are not eligible to participate in the study:

1. Epilepsy and currently on medication.
2. Clinically significant abnormalities in 12 lead ECG, in the opinion of the Investigator.
3. Breastfeeding or pregnant at Screening or planning to become pregnant at any time during the study.
4. Intolerable amifampridine-related side effects
5. Treatment with an investigational drug (other than amifampridine) or device while participating in this study.
6. Any medical condition that, in the opinion of the Investigator, might interfere with the patient's participation in the study, poses an added risk for the patient, or confound the assessment of the patient.

	MSK-003	Page 22
---	---------	---------

8.2.3 Removal of Patients from Treatment or Assessment

Patients may withdraw their consent to participate in the study or to receive treatment with IP at any time without prejudice. The Investigator must withdraw from the study or from treatment with IP any patient who requests to be withdrawn. A patient's participation in the study or treatment with IP may be discontinued at any time at the discretion of the Investigator and in accordance with his or her clinical judgment.

Catalyst must be notified of all patient withdrawals from the study or from treatment with IP as soon as possible. Catalyst also reserves the right to discontinue the study at any time for either clinical or administrative reasons and to discontinue participation by an individual Investigator or site for poor enrollment or noncompliance.

Reasons for which the Investigator or Catalyst may withdraw a patient from the study treatment include, but are not limited to, the following:

- Patient experiences a serious or intolerable AE;
- Patient requires medication prohibited by the protocol; and
- Patient becomes pregnant (refer to Section 9.4 for details on the reporting procedures to follow in the event of pregnancy).

Reasons for which the Investigator or Catalyst may withdraw a patient from the study include, but are not limited to, the following:

- Patient does not adhere to study requirements specified in the protocol;
- Patient was erroneously admitted into the study or does not meet inclusion criteria; and
- Patient is lost to follow-up.

If a patient fails to return for scheduled visits, a documented effort must be made to determine the reason. If the patient cannot be reached by telephone, a certified letter should be sent to the patient requesting contact with the Investigator. This information should be recorded in the study records.

The Investigator or designee must explain to each patient, before enrollment into the study, that for evaluation of study results, the patient's protected health information obtained during the study may be shared with Catalyst, regulatory agencies, and IRB/IEC/REB. It is the Investigator's (or designee's) responsibility to obtain written permission to use protected health information, per country-specific regulations, from each patient. If permission to use

protected health information is withdrawn, it is the Investigator's responsibility to obtain a written request, to ensure that no further data will be collected from the patient and the patient will be removed from the study.

8.2.4 Patient Identification

Each patient will be assigned a unique patient identifier (2 or 3 digits for the site and 2 or 3 digits for each patient enrolled). This unique identifier will be on all CRF pages.

8.3 Treatments

8.3.1 Treatments Administered

Catalyst or its designee will provide the study site with a supply of Investigational product: amifampridine tablets 10 mg at various intervals sufficient for the completion of the study.

Amifampridine will be provided in round, white-scored tablets and containing amifampridine phosphate formulated to be the equivalent of 10 mg amifampridine base per tablet. The product will be provided in bottles of bulk tablets to the pharmacy representative who will dispense an amount for each portion of the study, in a patient-specific labeled bottle.

[figure not shown]
8.3.2 Identity of Investigational Product

The chemical name of amifampridine phosphate is:

- 3,4-pyridinediamine, phosphate (1:1) diamino-3,4-pyridine, phosphate salt
- 3,4-diaminopyridine phosphate

The chemical structure is provided in [Figure 1](#).

Figure 1. Chemical Structure of Amifampridine Phosphate

8.3.3 Product Characteristics and Labeling

Drug product is formulated as a phosphate salt of amifampridine. Tablets were developed to provide the equivalent of 10 mg of amifampridine base for oral administration. Each tablet

	MSK-003	Page 24
---	---------	---------

contains amifampridine phosphate, microcrystalline cellulose, colloidal anhydrous silica, and calcium stearate. The bottles of tablets are labeled “Amifampridine Phosphate Tablets, 10 mg.”

The tablets are to be dispensed by the pharmacy representative into suitably sized pharmacy containers for patient use. Each bottle provided to patients will be labeled to include the compound name, site number, patient ID number, date dispensed, storage instructions, the statement ‘Caution – New Drug – Limited by Federal law to investigational use,’ trial number, manufacturer name and address, and area for instructions for use. Regional label requirements and translations should be used in accordance with local regulations.

8.3.4 Storage

At the study site, all IP must be stored under the conditions specified, 20-25° Celsius (C) and in a secure area accessible only to the designated pharmacist and clinical site personnel. All IP must be stored and inventoried, and the inventories must be carefully and accurately documented according to applicable national and local regulations, ICH GCP, and study procedures.

8.3.5 Directions for Administration

All doses of study drug will be taken as outpatients. Test medication should be taken every day at approximately the same time, at the dose and frequency instructed by Investigator.

The dose of amifampridine will be individually determined by the Investigator, within the bounds of a total daily dose of 30 mg to 80 mg, divided into doses taken 3 to 4 times per day as prescribed by the Investigator, based on optimal neuromuscular benefit determined from the Run-in Period from MSK-002 or may be modified as the discretion of the Investigator. The maximum single dose is 20 mg.

8.3.6 Method of Assigning Patients to Treatment Groups

All patients will receive open label amifampridine. Details on study drug preparation, dispensing medication will be included in the Pharmacy Manual.

8.3.7 Selection of Doses Used in the Study

Initially, the daily amifampridine dose will be the one that was determined at the end of the Run-in Period from MSK-002. The usual range is 30 to 80 mg total daily dose, given in 3 or 4 divided doses, with no single dose >20 mg. Safety of a single maximum dose of 20 mg is based on completed animal and *in vitro* pharmacology, PK, and toxicology studies.

	MSK-003	Page 25
---	---------	---------

8.3.8 Blinding

This is an open label study.

8.3.9 Treatment Compliance

Patients will be instructed to take study medication as directed and bring all IP containers and remaining test medication at each study visit. Patient compliance with the dosing regimen will be assessed by reconciliation of the used and unused IP. The quantity dispensed, returned, used, lost, etc., must be recorded on the medication dispensing log provided for the study.

8.3.10 Investigational Product Accountability

The study site is responsible for maintaining accurate records (including dates and quantities) of IP received, patients to whom IP is dispensed (patient-by-patient dose specific accounting), IP returned, and IP lost or destroyed. The Investigator, study site coordinator or designee must retain all unused or expired study supplies until the study monitor (on-site CRA) has confirmed the accountability data.

8.3.11 Return and Disposition of Clinical Supplies

Unused IP must be kept in a secure location for accountability and reconciliation by the study monitor. The Investigator or designee must provide an explanation for any destroyed or missing IP or study materials.

Unused IP may be destroyed on site, per the site's standard operating procedures, but only after Catalyst has granted approval for drug destruction. The monitor must account for all IP in a formal reconciliation process prior to IP destruction. All IP destroyed on site must be documented. Documentation must be provided to Catalyst and retained in the Investigator study files. If a site is unable to destroy IP appropriately, the site can return unused IP to Catalyst upon request. The return of IP or IP materials must be accounted for on a Study Drug Return Form provided by Catalyst.

All IP and related materials should be stored, inventoried, reconciled, and destroyed or returned according to applicable regulations and study procedures.

8.4 Prior and Concomitant Medications

All prescription and over-the-counter medications and herbal and nutritional supplements taken during the Long-Term study will be recorded on the designated CRF.

	MSK-003	Page 26
---	---------	---------

The Investigator may prescribe additional medications during the study, if the prescribed medication is not prohibited by the protocol. In the event of an emergency, any needed medications may be prescribed without prior approval, but the medical monitor must be notified of the use of any contraindicated medications immediately thereafter. Any concomitant medications added or discontinued during the study should be recorded on the CRF.

Medications that should be used with caution in this study are those that prolong QTc interval.

8.5 Dietary or Other Protocol Restrictions

8.5.1 Dietary Restrictions

There are no dietary restrictions for patients during any part of this study.

8.5.2 Contraception

Sexually active males and females of childbearing potential and their partners must use effective forms of contraception, such as condom for males or occlusive cap (diaphragm or cervical/vault caps) for females, during the study.

8.6 Safety Variables

Safety in this study will be determined from evaluation of AEs/SAEs, vital signs assessments, clinical laboratory assessments, ECGs, and physical examinations. Pregnancy testing is also required for females of childbearing potential. The timing of the required evaluations is described in the Schedule of Events in **Table 1** and in Section 11.

8.6.1 Adverse Events

The determination, evaluation and reporting of AEs will be performed as outlined in Section 9.

8.6.2 Vital Signs

Specific visits for obtaining vital signs are provided in **Table 1** and in Section 11. Vital signs will be measured while in a sitting position, after resting for 5 minutes, and include SBP and DBP measured in millimeters of mercury (mmHg), heart rate in beats per minute, respiration rate in breaths per minute. Weight (kg) and temperature in degrees C will also be measured. Clinically significant changes from baseline will be recorded as AEs.

8.6.3 Clinical Laboratory Assessments

Specific visits for obtaining clinical laboratory assessment samples are provided in [Table 1](#) for the tests required by Protocol. The scheduled clinical laboratory tests are listed in [Table 2](#). In brief, clinical laboratory evaluations are to be performed every 3 to 6 months. These tests can be performed more frequently at the discretion of the Investigator.

All abnormal clinical laboratory result pages should be initialed and dated by an Investigator, along with a comment for each abnormal result indicating whether or not it is clinically significant. Any abnormal test results determined to be clinically significant by the Investigator should be repeated (at the Investigator's discretion) until the cause of the abnormality is determined, the value returns to baseline or to within normal limits, or the Investigator determines that the abnormal value is no longer clinically significant.

Each clinically significant laboratory result should be recorded as an AE. The diagnosis, if known, associated with abnormalities in clinical laboratory tests that are considered clinically significant by the Investigator will be recorded on the AE CRF.

Table 2 Clinical Laboratory Tests

Blood Chemistry	Hematology	Urine Tests	Other
Albumin	Hemoglobin	Appearance	Pregnancy test, if applicable
Alkaline phosphatase	Hematocrit	Color	
ALT (SGPT)	WBC count	pH	
AST (SGOT)	RBC count	Specific gravity	
Direct bilirubin	Platelet count	Ketones	
Total bilirubin	Differential cell count	Protein	
BUN		Glucose	
Calcium		Bilirubin	
Chloride		Nitrite	
Total cholesterol		Urobilinogen	
CO ₂		Hemoglobin	
Creatine phosphokinase			
Creatinine			
Glucose			
GGT			
LDH			
Phosphorus			
Potassium			
Total protein			
Sodium			
Uric acid			

	MSK-003	Page 28
---	---------	---------

ALT, alanine aminotransferase; AST, aspartate aminotransferase; BUN, blood urea nitrogen; CO₂, carbon dioxide; GGT, gamma-glutamyl transferase; LDH, lactate dehydrogenase; RBC, red blood cell; SGOT, serum glutamic-oxaloacetic transaminase; SGPT, serum glutamic-pyruvic transaminase; WBC, white blood cell.

8.6.4 Pregnancy Testing

Female patients of childbearing potential will have a urine pregnancy test at the end of the double blind period on Day 10 and at other time points specified in the Schedule of Events ([Table 1](#)) and in Section 11. Female patients with a positive pregnancy test at end of the double-blind study are not eligible for enrollment. Additional pregnancy tests will be performed at any visit in which pregnancy status is in question.

Refer to Section [9.4](#) for details on the reporting procedures to follow in the event of pregnancy.

8.6.5 Electrocardiogram (ECG)

A standard 12-lead safety ECG (single tracing) will be recorded with the patient resting comfortably in the supine position at the time points specified in the Schedule of Events ([Table 1](#)) and in Section 11. Clinically significant changes from baseline will be recorded as AEs.

8.6.6 Physical Examination

A complete physical examination is to be performed at each clinic visit or, if applicable, at early discontinuation from the study. Complete physical examination will include assessments of general appearance as well as the following:

- Head
- Eyes
- Ears
- Nose
- Throat
- Cardiovascular
- Dermatologic
- Lymphatic
- Respiratory

	MSK-003	Page 29
---	---------	---------

- Gastrointestinal
- Musculoskeletal

Body weight will be measured with each physical examination throughout the study.

Other body systems may be examined. Clinically significant changes from baseline will be recorded as AEs.

8.7 Efficacy Variable

Every 3 or 6 months, each patient will be assessed with the MG-ADL questionnaire.

8.7.1 Myasthenia Gravis-Specific Activities of Daily Living (MG-ADL)

The MG-ADL is a self-report scale designed to assess the patient's MG symptoms and functional performance of activities of daily living. The MG-ADL consists of 8 items (derived from symptom-based components of the original 13-item Quantitative Myasthenia Gravis test) to assess disability secondary to ocular (2 items), bulbar (3 items), respiratory (1 item) and gross motor or limb (2 items) impairment related to effects from MG ([Appendix 1](#)). Each of the 8 items is rated using a response scale ranging from 0 (normal) to 3 (most severe). Lower scores indicate better functional performance. In this trial, the recall period for MG-ADL will be the preceding 30 days.

9 REPORTING ADVERSE EVENTS

9.1 Adverse Events

For this protocol, a reportable AE is any untoward medical occurrence (e.g. sign, symptom, illness, disease or injury) in a patient administered the IP or other protocol-imposed intervention, regardless of attribution. This includes:

- AEs not previously observed in the patient, that emerge during the study.
- Pre-existing medical conditions judged by the Investigator to have worsened in severity or frequency or changed in character during the study.
- Complications that occur as a result of non-drug protocol-imposed interventions.

An adverse drug reaction is any AE for which there is a reasonable possibility that the IP caused the AE. "Reasonable possibility" means there is evidence to suggest a causal relationship between the IP and the AE.

	MSK-003	Page 30
---	---------	---------

Whenever possible, it is preferable to record a diagnosis as the AE term rather than a series of terms relating to a diagnosis.

All non-serious AEs, even those which began under Protocol MSK-002, will be reported from the end of the double-blind study (MSK-002) through the termination visit or at the early termination visit and will be recorded on the AE page of the eCRF. All SAEs will be reported. The criteria for determining, and the reporting of SAEs is provided in Section 9.2.

The Investigator should follow all unresolved AEs until the events are resolved or stabilized, the patient is lost to follow-up, or it has been determined that the study treatment or participation is not the cause of the AE. Resolution of AEs (with dates) should be documented on the appropriate CRF page(s) and in the patient's medical record.

The Investigator responsible for the care of the patient or qualified designee will assess AEs for severity, relationship to IP, and seriousness (refer to Section 9.2 for SAE definition). Severity (as in mild, moderate or severe headache) is not equivalent to seriousness, which is based on patient/event outcome or action criteria usually associated with events that pose a threat to a patient's life or functioning. Seriousness (not severity) serves as a guide for defining regulatory reporting obligations.

The Investigator will determine the severity of each AE using grades defined in Table 3 (the event will be recorded on the source documents and AE CRF). Events that are Grades 4 and 5 are serious events and require completion of both an SAE form and AE CRF.

Table 1 Categories of Severity of Adverse Events

Severity	Description	
Grade 1	Mild; asymptomatic or mild symptoms; clinical or diagnostic observations only; intervention not indicated.	
Grade 2	Moderate; minimal, local or noninvasive intervention indicated; limiting age-appropriate instrumental ADL*.	
Grade 3	Severe or medically significant but not immediately life-threatening; hospitalization or prolongation of hospitalization indicated; disabling; limiting self-care ADL**.	
Grade 4	Life-threatening consequences; urgent intervention indicated.	Note: Grade 4 and 5 adverse events should always be reported as serious adverse events
Grade 5	Death related to AE.	

Activities of Daily Living (ADL)

* Instrumental ADLs refer to preparing meals, shopping for groceries or clothes, using the telephone, managing money, etc.

**Self-care ADLs refer to bathing, dressing and undressing, feeding self, using the toilet, taking medications, and not bedridden.

The Investigator will suggest the relationship of an AE to the IP and will record it on the source documents and AE CRF, using the relationship categories defined in [Table 4](#).

Table 2 Description of Relationship to Adverse Event Categories

Relationship Category	Description
Not Related	
Exposure to the IP has not occurred
 
OR
 
The administration of the IP and the occurrence of the AE are not reasonably related in time
 
OR
 
The AE is considered likely to be related to an etiology other than the use of the IP; that is, there are no facts [evidence] or arguments to suggest a causal relationship to the IP.

Possibly Related	
The administration of the IP and the occurrence of the AE are reasonably related in time
 
AND
 
The AE could be explained equally well by factors or causes other than exposure to the IP.

Probably Related	
The administration of IP and the occurrence of the AE are reasonably related in time
 
AND
 
The AE is more likely explained by exposure to the IP than by other factors or causes.

In order to classify AEs and diseases, preferred terms will be assigned by the sponsor to the original terms entered in the CRF, using Medical Dictionary for Regulatory Activities (MedDRA) terminology.

9.2 Serious Adverse Events

A serious adverse event is any untoward medical occurrence that at any dose meets 1 or more of the following criteria:

- Is fatal
- Is life threatening
 - *Note: Life-threatening refers to an event that places the patient at immediate risk of death. This definition does not include a reaction that, had it occurred in a more severe form, might have caused death*
- Requires or prolongs in-patient hospitalization

	MSK-003	Page 33
---	---------	---------

- Results in persistent or significant disability or incapacity
- Is a congenital anomaly or birth defect, that is, an AE that occurs in the child or fetus of a patient exposed to IP prior to conception or during pregnancy
- Is an important medical event or reaction.

The reporting period for SAEs begins after informed consent is obtained for the current MSK-003 study and continues through 4 weeks after the last visit.

Any SAE, whether or not considered related to study drug, must be reported within 24 hours of knowledge of the event by forwarding (fax, email) the study-specific SAE Report Form to Catalyst. The Investigator should not wait to collect information that fully documents the SAE before notifying Catalyst. As additional information becomes available, including but not limited to the outcome of the SAE and any medication or other therapeutic measures used to treat the event, it must be reported within 24 hours in a follow-up report.

The Investigator should follow all unresolved SAEs until the events are resolved or stabilized, the patient is lost to follow-up, or it has been determined that the study treatment or participation is not the cause of the AE. Resolution of AEs (with dates) should be documented in the CRF and in the patient's medical record.

For some SAEs, Catalyst may follow up by telephone, fax, email, and/or a monitoring visit to obtain additional case details deemed necessary to appropriately evaluate the SAE report (e.g. hospital discharge summary, consultant report, autopsy report).

At the last scheduled visit, the Investigator should instruct each patient to report any subsequent SAEs that the patient's personal physician(s) believes might be related to prior study treatment.

The Investigator should notify Catalyst of any death or SAE occurring at any time after a patient has discontinued, or terminated study participation, if felt to be related to prior study treatment. Catalyst should also be notified if the Investigator should become aware of the development of cancer, or of a congenital anomaly, in a subsequently conceived offspring of a patient that participated in this study.

Reporting of SAEs to the IRB/IEC/REB will be done in compliance with the standard operating procedures and policies of the IRB/IEC/REB and with applicable regulatory requirements. Adequate documentation must be provided showing that the IRB/IEC/REB was properly and promptly notified as required.

	MSK-003	Page 34
---	---------	---------

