In general, all categories that appear on the CRF and in summary table templates will be reported even if no patients reported that category (e.g., if there are no patients of a particular race). The “Missing” category displayed for categorical variables in summary table templates will only be displayed if missing observations are present. If no observations meet the criteria for inclusion in a data display (e.g., if there are no SAEs), the table or listing will be generated with a line in the body of the listing such as “None reported.”

No imputation will be conducted for the missing data.

3.1.4 *Sub-group Analyses*

All safety endpoints will be analyzed by MG type: MuSK-MG and AChR-MG.

3.2 *Subject Disposition, Demographics, Baseline Characters and Study Drug Compliance*

3.2.1 *Patient Disposition*

Study completion status will be summarized for all patients. The duration of treatment will be summarized for treated patients. Categories summarized will include patients who were planned, screened, screen failure, enrolled, received study drug, completed the study, were lost to follow-up, or withdrew early. Reasons for screen failure and withdrawal will be summarized.

3.2.2 *Protocol Deviations*

Individual protocol deviations will be presented in a data listing.

3.2.3 *Demographics and Baseline Characters*

Demographic characteristics of all patients enrolled will be summarized descriptively. The summary will include age, gender, race/ethnicity, height, weight.

3.2.4 *Study Drug Exposure*

The treatment duration (day), the total dose (mg) of study drug administered, average daily dose of study drug, and study drug compliance (%) will be tabulated.

- Treatment Duration (day) is calculated as The Last Dose Date – The First Dose Date +1. If the last dose date is missing, then the last visit date will be used.
- Total Dose (mg) will be calculated as the sum of the daily dose (mg) over the Treatment Duration, considering different doses during individual time periods within the study, as documented in the IP Accountability eCRF page.
- Average Daily Dose (mg) will be calculated as Total Dose (mg) / Treatment Duration (day). This will be calculated considering each time period and Daily dose during that period, as documented in the IP Accountability eCRF page.
- Study Drug Compliance (%): $100 \times \text{Total Dose Taken (mg)} / \text{Total Dose Prescribed (mg)}$

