3.5 Key Data Items

Study Analysis Population Definition:

- All Subjects: All subjects, including screening failures, who provided clinical information in the database.
- Safety Population: All enrolled subjects who receive at least one dose of study drug.

Important Derived Variables:

- Age (in year) = (Screening Date – Date of Birth +1)/365.25.
- Prior Medications and Treatments: The medications and treatments started before enrolled to the study (date of Informed Consent signed)
- Concomitant Medication and Treatments: The medications and treatments started on or after the date of Informed Consent signed
- Baseline: All safety measurements collected at Day 1 or before the first dose of study drug will be used as baseline
- Post Baseline Visit: follow up visit of 6, 9, 12, 15, 21, 27, 33 and 39 months after baseline and etc, or unscheduled visit after first dose of the study drug
- Study Day for follow-up visit: The visit date – Baseline date +1
 - o Follow-up visit at 3 months: The visit that is closest to study day 91
 - o Follow-up visit at 6 months: The visit that is closest to study day 183
 - o Follow-up visit at 12 months: The visit that is closest to study day 365
 - o Follow-up visit at 15 months: The visit that is closest to study day 456
 - o Follow-up visit at 21 months: The visit that is closest to study day 640
 - o Follow-up visit at 27 months: The visit that is closest to study day 822
 - o Follow-up visit at 33 months: The visit that is closest to study day 1005
 - o Follow-up visit at 39 months: The visit that is closest to study day 1187
- Duration of Disease (year):
(Date of Informed Consent signed – Date of original Diagnosis +1) / 365.25
- Study drug compliance (%): $100 \times \text{Total Dose (mg)} / \text{Total Prescribed Dose (mg)}$, where total dose taken will be calculated as (Dispensed # - Retuned # - Lost #) $\times 10$ mg (refer to CRF IP Accountability page (DA domain), and the total prescribed dose is collected at each IP accountability CRF (EX domain))
- Treatment emergent Adverse Events (TEAE): All AEs reported in this study are TEAE

Formulas of Metric Conversion:

- 1 inch = 2.54 cm
- 1 lb = 0.4536 kg
- $^{\circ}\text{C} = (^{\circ}\text{F} - 32) \times 5/9$

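### The SAP counts every reported AE as treatment-emergent and sets no cut-off after the last dose, so events arising well after drug is stopped can enter the primary TEAE percentages

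*Protocol*

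**What the plan says.** The protocol synopsis makes TEAE incidence, including SAEs, the primary safety measure and restricts the safety analysis to TEAEs. The protocol never defines the term. Protocol 13.7 lets the SAP prevail where the two differ, so the SAP definition governs: "All AEs reported in this study are TEAE" (SAP 3.5). SAP 3.3.2 repeats the rule and justifies it by the fact that patients were already taking the drug when they enrolled.

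The reporting periods are set in the protocol:

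- Non-serious AEs are reported "through the termination visit or at the early termination visit" (Protocol 9.1).
- For SAEs of any causality, reporting "continues through 4 weeks after the last visit" (Protocol 9.2).
- Separately, the investigator is to notify the sponsor of deaths and SAEs "occurring at any time after a patient has discontinued, or terminated study participation, if felt to be related" to study treatment (Protocol 9.2). This has no time limit.

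None of these refers to the last dose. Protocol 8.2.3 separates stopping drug from leaving the study: "The Investigator must withdraw from the study or from treatment with IP any patient who requests to be withdrawn". It also gives separate lists of reasons for each. Exposure, by contrast, does end with dosing: "Treatment Duration (day) is calculated as The Last Dose Date" (SAP 3.2.4).

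**The concern.** A treatment-emergent definition needs a start and an end. Prior exposure is a sensible reason for counting events from entry. It says nothing about events that begin after the drug has been stopped.

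With no end date, a patient who stops drug but keeps attending goes on contributing events labelled treatment-emergent while unexposed. The study is single-arm and descriptive, so the TEAE tables are its main result and no control group offsets the effect. A reader of T06 to T10 would take the percentages to describe time on, or shortly after, amifampridine. For some patients they would also cover months without it.

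**Working it through.** The documents give no figure on this point to reproduce. The check compares the rules and then gives a sense of scale.

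**Step 1: what can be counted off drug.** Take a patient who stops drug at some date and stays in the study.

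| Event | Collected until | Counted as TEAE under the SAP? |
|---|---|---|
| Non-serious AE | Termination or early termination visit | Yes, however long after the last dose |
| SAE, any causality | Last visit + 28 days | Yes, however long after the last dose |
| Death or related SAE after participation ends | No limit on notification | Not stated |

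The first two rows follow directly from the text. The third does not: the documents do not say whether such notifications reach the clinical database before the single lock in SAP 3.4.

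**Step 2: days involved.** Visit days are from SAP 3.1.2. Suppose drug stops just after Month 15 (day 456) and the last visit is Month 21 (day 640).

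- Off-drug days counted for any AE: 640 − 456 = 184.
- Off-drug days counted for SAEs: 184 + 28 = 212.
- Days removed by a cut-off at last dose + 28 days: 184 − 28 = 156 for non-serious AEs and 212 − 28 = 184 for SAEs.

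**Step 3: effect for one such patient.** Use P(at least one SAE by day d) = 1 − exp(−rate × d/365.25), with the same rate on and off drug. The rates are assumed; the documents give none. The cut-off day is 456 + 28 = 484, and the present rule counts to 640 + 28 = 668.

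| Assumed rate per patient-year | To day 484 | To day 668 | Difference |
|---|---|---|---|
| 0.05 | 6.4% | 8.7% | 2.3 points |
| 0.10 | 12.4% | 16.7% | 4.3 points |
| 0.30 | 32.8% | 42.2% | 9.4 points |

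Each such patient therefore adds an expected 0.02 to 0.09 patients to the SAE count. The groups are analysed separately, so one extra patient is 1/60 = 1.7 points in the MuSK-MG group and 1/10 = 10 points in the AChR-MG group, at the planned sizes.

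**Step 4: the SAE-only tail.** This is a separate matter of collection. The 28 days after the last visit make up 28/(d + 28) of a patient's SAE reporting period: 23.5% if the last visit is day 91, 9.3% at day 274, 4.2% at day 640 and 2.3% at day 1187. With the last dose at the last visit and the same assumed rates, the tail adds:

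- 0.37, 0.71 and 1.82 points to SAE incidence for a 274-day participant;
- 0.33, 0.55 and 0.86 points for a 1187-day participant.

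Applied to 60 patients, that is about 0.2 to 1.1 patients. Non-serious AEs have no such tail.

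**The case against.** The strongest reply is that little is at stake. Planned outputs are crude percentages of patients, and no hypothesis is tested. Off-drug time can add a patient to a TEAE percentage but never remove one, so the error is toward over-counting harm. All AEs are listed (DL06a) and T09 tabulates by relationship. The protocol's own definition of an unrelated event includes one not reasonably related in time to dosing. The SAP sends discontinued patients to an early termination visit, and Table 1 marks treatment at every visit, so long off-drug attendance may be rare. All of this stands and limits the size. It does not supply the missing end date.

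Several stronger readings are tempting but not supported:

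- *Follow-up ends at different points by seriousness.* These are reporting periods. For unresolved events the investigator "should follow all unresolved AEs until the events are resolved or stabilized", with further stopping conditions, and the same rule applies to SAEs.
- *The related share of SAEs is inflated.* That requires late notifications to reach the tables, which the documents do not say.
- *Event counts and T03 exposure stop at different times, which corrupts a rate.* The different end dates are real, but no planned statistic divides events by exposure.
- *The effect is 1.1 to 3.4 points.* This follows if 7 of 70 patients stop at day 274 and stay to day 1187, with 0.05 to 0.20 SAEs per patient-year. At 0.05, 7 × (0.150 − 0.037) = 0.79 patients; at 0.20, 7 × (0.478 − 0.139) = 2.37; each is then divided by 70. The arithmetic is right, but the scenario is an assumed extreme.

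The mismatch could also run the other way. Protocol 11.2 provides for 180 days of drug at Month 39, while SAP 3.1.2 treats Month 39 as the end-of-study visit for completers. If that supply were taken, on-drug time could outlast non-serious reporting by up to 180 days and SAE reporting by up to 180 − 28 = 152 days. Those passages need to be reconciled.

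**Conclusion.** The point holds in a limited form. The SAP's treatment-emergent rule has no end, and its stated reason covers only the start. AEs up to the termination visit, and SAEs up to 4 weeks after the last visit, can be counted as TEAEs although they arise well after the last dose. The direction is certain: crude TEAE and treatment-emergent SAE percentages can only go up.

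The size is unknown because it depends on how many patients stop drug and remain in the study. It is probably small for patients dosed up to their last visit and larger for those who stop early and stay. The percentages in the working rest on assumed, constant SAE rates that are equal on and off drug; they show scale and are not estimates. Related SAEs notified after participation ends might also enter the tables, but that is a possibility only.

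**What to change.** In SAP 3.3.2 and 3.5, define a TEAE as an AE with onset up to the last MSK-003 dose date + 28 days, or up to the end of collection for that event type if earlier. The 28 days match the length of the protocol's SAE period after the last visit; the choice is a convention. Tabulate T06 to T10 on that window and put later events in a separate post-treatment listing, including any related SAEs notified late that reach the database. State what happens when the last dose date is missing. Borrowing SAP 3.2.4's substitution of the last visit date would leave the SAE cut-off where it is now for those patients.

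Add a note to the tables that non-serious AEs are collected only to the termination visit and SAEs for 4 weeks longer, so the serious share of events after the last visit cannot be interpreted. An SAP rule cannot tabulate events that were never collected. Removing that asymmetry would need a change to Protocol 9.1.

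The cost is a short change to the SAP definition, a date comparison in the AE dataset, one listing and one table note. The last dose date is already needed for exposure. The downside is that a few late events move from the main tables to a listing, where they stay visible.
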